2.2.1.2.4 Pharmacodynamics/Biomarkers²⁴

Pharmacodynamic (PD) measures included lymphocyte subsets and cytokines. The response to blinatumomab was characterized by peripheral B-cell depletion, T-cell activation and redistribution as well as transient cytokine elevation. Consistent PD profiles were observed across clinical trials following the cIV regimen.

T-cell dynamics: Following blinatumomab cIV infusion, peripheral T-cell counts initially declined within 1 to 2 days to very low levels, a phenomenon described as redistribution from periphery to tissues. After the initial decline, T-cells started to increase and reached baseline levels in about 14 days. Increase of T-cell counts above baseline was found in some subjects. There was no difference between the dynamics of CD4⁺ and CD8⁺ T cells. A high inter-individual variability was observed in T-cell baseline levels. The time to return to baseline was variable across subjects (10 to 30 days).

B-cell Dynamics: B-cell counts in peripheral blood decreased rapidly and became undetectable during treatment at doses $\geq 5 \mu\text{g}/\text{m}^2/\text{day}$ (or $9 \mu\text{g}/\text{day}$) in most subjects. No recovery of B-cell counts was observed during the drug-free period between treatment cycles. Incomplete depletion of B cells was observed at doses of 0.5 and $1.5 \mu\text{g}/\text{m}^2/\text{day}$. High inter-individual variability was found in baseline B-cell counts. Associated with the B-cell depletion, decreases in immunoglobulin (Ig) levels have been observed. Long-term Ig levels were measured in 6 MRD-positive ALL subjects treated with blinatumomab. Partial to complete recovery of IgM and IgG levels and incomplete recovery of IgA were observed during the long-term safety follow-up period.³⁴

Cytokine Dynamics: The measured cytokines were TNF- α , IL-2, IL-6, IL-8, IL-10, IL-12, IL-4, and IFN- γ . Transient elevation of cytokines was observed in some subjects in the first 2 days following the blinatumomab infusion. The elevated cytokine levels returned to baseline within 24 to 48 hours during the infusion period. In subsequent treatment cycles, cytokine elevation was only observed in few subjects with much less intensity. The magnitude of cytokine elevation

trended higher at higher doses. The inter-subject variability in cytokine elevation was large.

See Section 8.1.1 for drug information.

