9. BIOMARKER, CORRELATIVE, AND SPECIAL STUDIES

9.1 Overview

Mandatory research bone marrow aspirates (40 cc-4 green top tubes-sodium heparin) and research peripheral blood specimens (preferred 100 cc [minimum 60 cc]-10 (min 6) green top tubes-sodium heparin) will be obtained (preferentially on the same day): at baseline (1-7 days prior to the initiation of study treatment; up to 14 days prior to the initiation of study treatment allowed for patients requiring prephase treatment), prior to first dose of nivolumab / ipilimumab in cycle 1 (day 8-11 +/- 4 days), at the end of cycles 1 and 2 (day 29-35), and every 3-4 months up to 1 yr, or at the time of relapse or off study.

Additional research peripheral blood specimens (preferred 40 cc [minimum 30 cc]- 3 or 4 green top tubes) will be collected in cycle 1 (days 1, 15, and 22; all ± 3 days), and prior to cycle 2 (day 40-42 of cycle 1).

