¹¹ All patients should have baseline ECG. Baseline ECHOCardiogram is required for patients with a history of CHF, or at risk because of underlying cardiovascular disease (e.g history of angina, heart attack, or prior cardiovascular interventions or findings), history of cardiac arrhythmias, or exposure to cardiotoxic drugs (e.g anthracyclines, cyclophosphamide, or others) as clinically indicated. Any patient with heart arrhythmia or ischemic changes on baseline ECG should have baseline ECHOCardiogram. In addition, any patient who develop symptoms or signs of CHF, MI, cardiomyopathy, or myositis in the course of the study, should have repeat EKG, ECHOCardiogram, as well as cardiac evaluation including lab tests, CPK, troponin, and cardiology consultations as clinically indicated.

¹² Bone marrow aspirate and biopsy to assess disease status and response to therapy will be performed at baseline (after pre-registration and prior to registration), at the end of cycle 1 and 2 (day 29-day 35), and every 3-4 months thereafter up to 1 yr, any time relapse is suspected or off treatment. Additional bone marrow aspirates for research purposes only will be performed in cycle 1 within 3 days of the first nivolumab/ipilimumab administration (between days 8-11 of cycle 1 but can be delayed if nivolumab and/or ipilimumab administration is delayed in Cycle 1 as per Section 5.3.2 and 5.3.3) prior to nivolumab administration. Each time bone marrow assessment is performed to assess disease status, the flow cytometry studies for MRD assessment will be performed.

¹³ All patients should have baseline CSF assessment prior to enrollment on the study. Administration of intrathecal chemotherapy is required when LP is performed with a choice of agent (ara-C or MTX or both) and dose as per institutional standard of practice. Subsequent IT chemotherapy administration for CNS prophylaxis should be performed at the end of blinatumomab administration in cycles 1 and 2 (day 29-35) and the determination of need for subsequent CSF prophylaxis will be per investigator's discretion.

¹⁴ Each time bone marrow is performed for disease status assessment additional 40 cc of the bone marrow should be collected for research studies. Additional bone marrow aspirate for research purpose only will be performed in cycle 1 (between days 8-11) prior to nivolumab administration.

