¹⁵ Peripheral blood 100 cc (min 60 cc) for research studies will be collected at baseline (after pre-registration and prior to registration), prior to first dose of nivolumab / ipilimumab in cycle 1 (-3 days), at the end of cycle 1 and 2 (day 29-35), and every 3-4 months up to 1 yr, or at the time of relapse or off treatment. Additional research peripheral blood 40 cc (min 30 cc) will be collected in cycle 1 (day 1, 15, 22; all ± 3 days), on day 1 (-3 days) of cycle 2.

¹⁶ Assessments for toxicity/adverse events are to continue for 100 days after the last dose of nivolumab or ipilimumab, whichever was administered last. These may occur by phone for subjects no longer being seen at the institution; however, an in-person clinic visit may be needed to confirm event resolution and/or to effectively evaluate possible immune-related events. In addition, all patients who go onto allo-HSCT following the completion of treatment on the study will undergo continuous monitoring for acute grade 3-4 graft versus host disease and post-transplant non-relapse mortality for the first 100 post-transplant days. Subjects must be told of follow-up requirements at study entry.

¹⁷ Subjects will be followed about every 3 months for disease status and survival. Information about subsequent treatment received and response will be collected.

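### Section 9.1 lets the pre-nivolumab research sample precede the day 8 blinatumomab step, and with calendar footnote 15 lets day 1 blood be drawn on drug; the sampling windows need to be reconciled

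*Combined protocol and SAP*

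**What the plan says.** All references are to the combined protocol and SAP.

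**Pre-nivolumab marrow and blood.**
- Section 9.1: "prior to first dose of nivolumab / ipilimumab in cycle 1 (day 8-11 +/- 4 days".
- Section 10, footnote 12: the research marrow "will be performed in cycle 1 within 3 days of the first nivolumab/ipilimumab administration", placed "between days 8-11 of cycle 1 but can be delayed if nivolumab and/or ipilimumab administration is delayed in Cycle 1". Footnote 14 says it "will be performed in cycle 1 (between days 8-11) prior to nivolumab administration". The calendar table also asks for it no more than 3 days ahead of nivolumab.
- Section 10, footnote 15 (blood): "prior to first dose of nivolumab / ipilimumab in cycle 1 (-3 days".
- Appendix F: the cycle 1 day 8 row allows plus 3 days only.

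**Cycle 1 day 1 blood.**
- Section 9.1: this sample, with those of days 15 and 22, "will be collected in cycle 1 (days 1, 15, and 22; all ± 3 days".
- Section 10, footnote 15: it "will be collected in cycle 1 (day 1, 15, 22; all ± 3 days), on day 1 (-3 days) of cycle 2". The one-sided limit at the end belongs to cycle 2.
- Appendix F: the cycle 1 day 1 row allows minus 3 days only.

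Blinatumomab is stepped up on day 8, and the first nivolumab dose is scheduled for day 11 (Sections 5.1 and 5.3.2).

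**The concern.** Sections 5.1 and 13.1 give the ten-day blinatumomab run-in a scientific purpose: to show what blinatumomab does to immune measures before checkpoint inhibitors are added. The pre-nivolumab sample is the one that captures this. If some patients are sampled at 9 µg/day on days 4 to 7 and others after the step to 28 µg/day, one label covers two dose conditions.

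The day 1 blood raises a similar problem. Section 2.2.1.2.4 reports that "peripheral T-cell counts initially declined within 1 to 2 days to very low levels", and that cytokines rise transiently in some patients over the first 2 days. Section 2.4.1 dates the start of the T-cell fall to within hours. A draw after the infusion starts is not a pre-dose value, yet it would carry the same label as one.

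Section 13.8.1 models change from baseline with fixed effects for time point. It has no rule for assigning a sample to a time point by when it was actually taken. Sites are sent to both Section 9.1 and the calendar, and they complete the Appendix F form, so they can comply with one text while departing from another.

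**Working it through.** The plan states no design figure to reproduce. The check is interval arithmetic on the stated days, taking day 1 as the start of infusion.

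**Windows when nivolumab is first given on day 11**

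| Source | Day 1 blood | Pre-nivolumab sample |
|---|---|---|
| Section 9.1 | 3 days before, to 1 + 3 = day 4 | 8 − 4 = day 4, to 11 + 4 = day 15 |
| Calendar footnote 15 (blood) | same as Section 9.1 | 11 − 3 = day 8, to day 11 |
| Calendar table, footnotes 12 and 14 (marrow) | not applicable | days 8 to 11 |
| Appendix F | 3 days before, to day 1 | day 8, to 8 + 3 = day 11 |

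**Pre-nivolumab sample.** The requirement that it precede the first dose trims the Section 9.1 window to days 4 to 11, which is 11 − 4 + 1 = 8 permitted days. Of these, days 4 to 7 (7 − 4 + 1 = 4 days) fall before the step. The precedence requirement closes the late side only. The calendar and Appendix F both start at day 8, so Section 9.1 alone permits days 4 to 7.

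**Day 1 blood.** Section 9.1 and footnote 15 permit 3 + 1 + 3 = 7 days. Three of them (days 2, 3 and 4) are on drug, and a day 1 draw may fall either side of the infusion start. Appendix F removes days 2 to 4 but is the only text that does.

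**When the first nivolumab dose moves.** Section 5.3.2 allows a delay to day 15, or otherwise to the next scheduled time around day 25.
- First dose on day 15: footnote 15 gives 15 − 3 = day 12 to day 15. Appendix F ends at day 11, so the two do not overlap.
- First dose on day 25: footnote 15 gives 25 − 3 = day 22 to day 25. Section 9.1 ends at day 15 and Appendix F at day 11, so neither overlaps with it.
- First dose on day 9, if the ± 2 days in calendar footnote 1 applies to the first dose: footnote 15 gives 9 − 3 = day 6 for blood, again before the step. The calendar marrow stays on days 8 to 11.

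The last case shows that tying the sample to nivolumab alone is not quite enough; a lower limit of day 8 is needed as well.

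These are counts of permitted days. They are not estimates of how many samples were taken on those days, which the documents do not report.

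**The case against.** The strongest reply is that little depends on this.

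- Change is measured from a separate baseline draw, taken 1 to 7 days before treatment (up to 14 with pre-phase treatment). A late day 1 blood does not corrupt that reference. This stands.
- The T-cell repertoire and transcriptome studies use pre-treatment, response and relapse samples (Sections 9.2.3.1 and 9.2.3.2). This stands, and leaves mainly flow cytometry and cytokines exposed.
- Section 13.8.1 calls these analyses descriptive and graphical, and Section 9.1.2 requires collection date and time to be recorded, so mistimed samples can be identified. That is true, but identifying one does not recover a pre-dose or post-step sample that was never drawn, and no reclassification is planned.
- The width has partial explanations. The upper 4 days match the permitted nivolumab delay from day 11 to day 15. For the blast studies, Sections 2.4.3 and 9.2.1.2 ask only for a sample within ten days of blinatumomab treatment and before checkpoint inhibitors, which days 4 to 7 satisfy. Neither explains why the calendar and worksheet say something else, and the heading of Section 9.2.1.2 itself points to week 2.
- The run-in has a second purpose, limiting overlapping toxicity (Section 5.1), which sampling times do not touch. This stands.

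**Conclusion.** The inconsistency is real and minor. For day 11 dosing, Section 9.1 stands alone in permitting a pre-nivolumab sample on days 4 to 7. Section 9.1 and footnote 15 together permit day 1 blood to day 4, against Appendix F. The consequence is possible mixing of treatment states under one label in exploratory flow cytometry and cytokine time-point analyses. Safety, MTD and response are unaffected.

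Three stronger readings are tempting and not supported:
- That the calendar contradicts Section 9.1 on the day 1 blood. It does not: footnote 15 repeats ± 3 days. Correcting Section 9.1 alone would leave the problem in the calendar.
- That a draw 3 days into infusion is at the T-cell trough. Section 2.2.1.2.4 puts return to baseline at about 14 days, while Section 2.4.1 says a few days. Such a sample is on drug, but its position relative to the trough is not established.
- That the modelled effects are biased. No share of affected samples is given, so bias is possible and not shown.

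The conclusion assumes that sites use the windows as written and that the analysis groups samples by nominal time point, as Section 13.8.1 reads.

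**What to change.** Reconcile Section 9.1, calendar footnote 15 and Appendix F to one window per sample:

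- **Cycle 1 day 1 blood:** up to 3 days before, and always before the blinatumomab infusion starts.
- **Pre-nivolumab marrow and blood:** within 3 days before the first nivolumab dose and not before day 8. The Appendix F row should move with a delayed first nivolumab dose, as footnote 12 already allows for the marrow.

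In Section 13.8.1, state that samples are classified by recorded collection time relative to infusion start, the day 8 step and the first nivolumab dose. This also settles day 8 draws, since neither the calendar nor the worksheet says whether they come before or after the step. It helps even for samples already collected.

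For patients given pre-phase dexamethasone, a draw up to 3 days before infusion can still fall during the steroid course, which need end only 24 hours before blinatumomab. The recorded time should therefore also be read against the end of pre-phase treatment.

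The cost is wording in three places plus Section 13.8.1, and slightly tighter scheduling. No extra samples are needed.

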9.1.1 Collection of specimens

All operating procedures for specimen collection, handling and storage are standardized. Common standardized operating procedures (SOPs) are described in Appendix E. The plan is to collect research PB (60-100 cc or 30-40 cc) and BM specimens (40 cc) from the patient at the time points indicated in Section 9.1 above and on the Study Calendar. Re-adjustment of the direction of bone marrow aspirate needle should take a place after each 5 cc is collected to prevent hemodilution. At the time of sample collection, tubes must be thoroughly mixed to prevent clotting. In the event that the baseline BM aspirate and biopsy was not successful or inevaluable, and subject cannot undergo a second BM aspirate and biopsy for any reason, including refusal, the subject will be allowed to be treated on study protocol as long as diagnosis can be confirmed by other means, including analysis of PB.

9.1.2 Handling and Shipping of Specimens

A unique subject identifier will be assigned to each subject by the coordinating center and will be used to label the samples. The protocol scientific investigator(s) analyzing the samples will be blinded as to the direct subject identifiers.

All specimens should be labeled with the patient's identification number (given at the time of registration), and study number. Sample collection date and time, and sample source (PB or BM) will be recorded on correlative studies collection worksheet (Appendix F) and copy included in delivery. All data will be kept in laboratory log.

Research blood and marrow aspirates will be sent to Johns Hopkins to the laboratory of [name]. [name] laboratory: [name]. [contact]. [name] e-mail: [contact]

At each sampling interval, BM and PB mononuclear cells (PBMC) will be processed via Ficoll density gradient centrifugation. The washed cells will be counted and viably cryopreserved using

a controlled-rate freezer with transfer to the vapor phase of liquid nitrogen for long-term storage. Please refer to the JHU Protocol for PBMC/Plasma (Appendix E).

- 9.1.2.1 Specimen collection/processing (JHU): The specimens collected at the Sidney Kimmel Comprehensive Cancer Center at Johns Hopkins should be delivered to the [name] laboratory immediately after collection.
- 9.1.2.2 Specimen collection / processing (Participating Sites). Other participating sites should collect PB and BM specimens as outlined in the protocol above. Participating sites will have two options:
- a) To process specimens following the SOP in Appendix E. Samples will be stored at each study site and will be batch shipped on dry ice based on arrangement with the participating site PI and [name] and upon request of the Study Chair they will be batch shipped to SKCCC. Samples will be shipped or delivered to [name] laboratory: [name]. [contact].
- b) If a participating site does not have the capability of processing the specimens as detailed in Appendix E, then specimens can be shipped overnight to [name] laboratory using cold shipping packages (boxes) provided by Fedex. Please notify the PI-[name], coordinating center research nurse and [name] laboratory of specimen shipment.

9.2 Methods

The overarching goals of exploratory correlative studies are to: a) characterize the effect of blinatumomab in combination with checkpoint inhibition on T cells particularly on their re-distribution, in vivo expansion, activation, and effector differentiation in both PB and BM compartment over time and in relation to the response to therapy; b) identify potential predictive biomarker candidates to guide improved selection of ALL patients who are more likely to benefit from addition of checkpoint inhibitors to blinatumomab therapy in the future; c) characterize the mechanisms of relapse / refractoriness to blinatumomab combined with checkpoint inhibition such as T-cell dysfunction or to identify alternative resistance mechanisms that could be employed by ALL cells to evade blinatumomab/checkpoint inhibition. These studies should provide critical information on the selection of best immune-therapeutic combinations for futures studies in ALL. The proposed exploratory correlative studies are as follows:

9.2.1 Flow cytometry studies

- 9.2.1.1 **Exploratory/Ancillary Correlative Studies #1: T-cell subsets distribution (CD4⁺, CD8⁺, T_{regs}, T_{effs}), their differentiation status and expression of co-signaling molecules and canonic transcription factors, NK cells, and B cells before and post-blinatumomab, and immune checkpoint inhibitor(s) therapy in both peripheral blood and the bone marrow microenvironment (Serial PB and BM samples collected at all time points as indicated in Section 9.1). We will perform multi-parameter flow cytometry on PB and BM specimens obtained at designated**

time points indicated in the Section 9.1 and on the Study Calendar to examine the effect of blinatumomab and checkpoint inhibition on T, NK and B cell dynamics in two different compartments in ALL patients. The analysis will be performed using three pre-determined panels of mAbs including but not limited to those specific for CD3, CD4, CD8, PD-1, CD45RA, CCR7, CD25, CD27, CD28, CD57, CD69, Ki-67, T-bet, CD95, CD127, FoxP3, HLA-DR, CTLA-4, TNFR11, TIM-3, LAG-3, CD160, 2B4, BTLA, KLRG-1, Eomes, Blimp-1, CD16, and CD56. This multi-parametric flow cytometry approach allows examination of different CD4⁺ and CD8⁺ T-cell subpopulations (expressing CD45RA, CCR7, CD27, CD28 and CD57), their expression of co-signaling molecules, proliferation (% Ki-67 positive cells) and activation status (CD69, HLA-DR and TNFR11) as well as phenotypic separation of human CD4⁺FoxP3⁺ T cells into three distinct subpopulations. Natural killer cells (NK), NK-T cells will be enumerated using CD16 and CD56 (NK/NK-T cells). Additionally kinetics and durability of B cell depletion (CD19) will be assessed. [name] (co-investigator) and his lab have extensive experience in characterizing different T cell subpopulations in leukemia patients at diagnosis, during and after chemotherapy, after allogeneic HSCT, and in follow up as published.⁷⁴ Our studies in AML clearly show differences in T cell distribution, activation status, and expression of different co-signaling molecules between the PB and BM and depending the disease status and response to therapy.⁷⁴

NOTE: See BIOASSAY TEMPLATE IN Appendix C.

9.2.1.2 **Exploratory/ Ancillary Correlative Laboratory Studies #2: Characterize the expression of co-signaling molecules on BM or PB ALL blasts prior to, during and after blinatumomab and checkpoint inhibition (Pre-treatment, week 2 Cycle 1 if feasible, at response assessment following Cycle 1 and/or 2, BM).** Flow cytometric studies will be performed on leukemia blasts (CD19/CD10/CD34 plus other leukemia specific marker) to examine for expression of co-stimulatory and co-inhibitory molecules such as PD-L1, B7-H3, VISTA, Gal-9, CD86, PVR, PVR2, OX40L, ICOSL at baseline, within 10 days of blinatumomab treatment (prior to first administration of checkpoint inhibitors), in non-responders following combination treatment after cycle 1 and/or 2, and at the time of relapse. Collected specimens will also serve to examine for other mechanisms of relapse or resistance such as CD19 loss.

9.2.2 Cytokine studies

9.2.2.1 **Exploratory/ Ancillary Correlative Laboratory Studies #3: Cytokine measurement.** As a part of PB and BM collection and mononuclear cell isolation we will collect plasma that will be used for the measurement of defined cytokines (IL-2, IL-6, IL-10, IFN- γ , TNF- α) to assess blinatumomab and checkpoint inhibitors-induced global T-cell activation. We will examine the levels of cytokines before and after treatment with blinatumomab and checkpoint inhibitors, including the levels of sCTLA-4 using a standard ELISA tests (Bio-Plex Pro Human Cytokine 8-Plex Immunoassay, Bio-Rad Laboratories, Inc; Human sCD152/CTLA-4 Platinum ELISA.

eBioscience).

9.2.3 Molecular studies

- 9.2.3.1 **Exploratory/ Ancillary Correlative Laboratory Studies #4: Immune Profiling of T cell Repertoire (pre-treatment, response assessment after Cycle 1 or 2 and at relapse, PB and BM).** The studies proposed will evaluate the TCR diversity in T cells isolated from PB and BM from patients before and after treatment with blinatumomab and checkpoint inhibitors. We will determine TCR diversity and clonal composition using a molecular and computational approach based on high-throughput DNA sequencing of rearranged TCR β CDR3 regions from T cell genomic DNA from Adaptive Biotechnologies. This approach allows direct measurement of the TCR β CDR3 region sequence diversity in any arbitrarily complex population of T cells, and also permits quantitative description of the clonal composition of the population. The [name] laboratory in collaboration with the [name] laboratory from Fred Hutchinson Cancer Research Center (FHCRC) have performed extensive monitoring and tracking of the TCR repertoires in patients undergoing alloHSCT.⁹⁹ We are utilizing an established multiplex PCR strategy to amplify the CDR3 region of the TCR, spanning the variable region formed by the junction of the V, D and J segments and their associated non-template insertions followed by Illumina-based sequencing methodology, a well-characterized methodology developed by Adaptive Technology (<http://www.adaptivebiotech.com/technology/>). Sequencing is followed by comprehensive bioinformatics analyses focused on determining the diversity of the T cell and B cell repertoires as well as the entropy and clonality of each repertoire consistent with previous studies. Through these ongoing studies we have developed substantial experience not only in using and analyzing DNA retrieved from unsorted PBMCs but also from sorted T cells subpopulations (naïve vs memory vs regulatory), paired PB and BM samples and as well from DNA retrieved from FFPE archived tissues.
- 9.2.3.2 **Exploratory/ Ancillary Correlative Laboratory Studies #5: Characterization of T cell transcriptional signature before and after treatment (pre-treatment, response assessment after Cycle 1 or 2 and at relapse, PB and BM).** For the analysis of T-cell gene expression profiles we will use the Human Prime View Gene Expression Array (<http://www.affymetrix.com>). Differentially-expressed genes and corresponding fold-changes will be analyzed using standard statistics and through the use of Ingenuity pathway analysis as described previously. We predict based on our previous work that several key co-stimulatory signaling pathways will be downregulated in CD8⁺ T cells retrieved from patients with leukemia in comparison to healthy controls and that these pathways will differ after blinatumomab, nivolumab and ipilimumab administration. We will also examine whether there is differential-expression of genes between CD8⁺ T cells in BM relative to those in circulation. These studies are likely to provide important insights into the T cell transcriptome in patients with ALL in particular as it relate to the immunomodulatory strategies to modulate their function. While analysis will focus on CD8⁺ T cells, as part of T cell isolation we are routinely sorting CD8⁺, CD4⁺, B cells, NK cells and tumor cells;

these other populations will be stored for future analysis. Given that recent studies suggest that mutant neo-epitopes provide potent targets of checkpoint inhibitors, stored tumor specimens may be used in the future for neo-antigen discovery studies.

The workflow of specimens for TCR sequencing (Adaptive Biotechnologies) and gene expression analysis have been optimized in [name] Laboratory. Briefly, CD8+ T cells from serial samples (at diagnosis and at the response assessment) will be FACS-purified from PB and or BM and DNA/RNA will be isolated and used for TCR deep sequencing and gene expression studies, respectively. To determine TCR diversity of T cells we are utilizing an established multiplex PCR strategy followed by Illumina-based sequencing methodology, a well-characterized methodology developed by Adaptive Technology (<http://www.adaptivebiotech.com/technology>). For gene expression studies, cDNA will be synthesized and amplified from total RNA will be hybridized to the Human Prime View Gene Expression Array (<http://www.affymetrix.com>) at JHU Deep Sequencing and Microarray Core.

